1.3 Secondary Study Endpoints

State the secondary endpoints to be measured in the study.

- Successful uptake and demonstrable utility of actigraphy and intermittent home-based blood pressure monitoring (HBPM) during and after pregnancy.
- Successful uptake and demonstrable utility of an enhanced smoking cessation intervention among women who smoke or have environmental smoke exposure.

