Physical Activity Monitoring. We will use a commercially available wrist-worn device, the Fitbit Charge 5, to monitor physical activity. This device has a long battery life of 7 days and is compatible with a wide variety of devices and operating systems and can differentiate type and duration of activity.

Weight Monitoring: We will use a commercially available digital scale, the Fitbit Aria Scale, to monitor participant weight. This device has a long battery life and is compatible with a wide variety of devices (including the Fitbit) and operating systems.

Home Blood Pressure Monitoring (HBPM). We will utilize the devices and methodology (including apps and central database) utilized in the BUMP 1 and 2 trials.^{81,82} Participants will be provided with a validated automated monitor (Microlife Watch BP Home).⁹⁵ They will be given training and written instructions for HBPM by the recruiting NFP visiting nurse. Participants will be asked to self-monitor their BP 3 times per week, to take 2 readings each time, and to recording readings on a study tracking log provided by the study. NFP visiting nurses will review the log at each visit. During pregnancy and the puerperium, elevated readings (defined as a blood pressure > 140/90 as per the CHAP trial)⁹⁶ will trigger a request from the app for a third reading. If a participant’s third reading is also elevated, the app will trigger a message to the participant to contact their local obstetric provider. After the puerperium and during the postpartum period a blood pressure > 150/100 will trigger a similar alert to their primary care provider. We will follow NFP protocols to establish contact with a primary care provider if the participant does not have one.

Family and maternal demographics. We will collect demographic information at baseline (before study visit 1) and at follow-up (after study visit 3). Participants will be asked to provide information about their pregnancy and household and complete two online packets of questionnaires, which will take about 15 to 20 minutes to complete. Participants will also be given the option to complete surveys on paper if that is their preference.

7.2.1 Visit 1 or Day 1 or Pre-test, etc.

Provide a description of what procedures will be performed on visit 1 or day 1 or pre-test in order of how these will be done. If your study only involves one session or visit, use this section only and indicate 7.2.2 as not applicable.

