Study Visit 1 (V1) as summarized in Table 1 will take place at the first home visit after informed consent has been obtained. At this visit, participants will receive “Getting Started” handouts that includes information on setting up the commercially available devices including a 1) a device that monitors physical activity daily for 6 months, 2) a digital scale that monitors weight once per week for 6 months, and 2) a home blood pressure monitor that monitors your blood pressure three times per week for 6 months. NFP visiting nurse will also measure carbon monoxide levels using a provided device at this study visit. During this visit, participants will also be asked to take part in a tobacco cessation program if they have used a nicotine product in the past 3 months. This includes the NFP visiting nurse providing an active referral to a national tobacco quit line and provide a handout on the benefits of and tips for quitting smoking during and or after pregnancy.

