7.2.2 Visit 2 or Day 2 or Post-test, etc. (If applicable)

Provide a description of what procedures will be performed on visit 2 or day 2 or post-test in order of how these will be done. If your study involves more than two sessions or visits replicate this section for each additional session or visit (e.g., 7.2.3, 7.2.4, etc.).

Study Visit 2 (V2) as summarized in Table 1 will take place about 1 to 2 months after the participants first study visit. At this visit, participants will receive “Physical Activity During Pregnancy” handouts that includes information on safely adding physical activity into their daily life from their visiting nurse. The NFP visiting nurse will also answer any questions participants have about physical activity and weight monitoring. The NFP visiting nurse will also review results and answer any questions about the results from participant home blood pressure monitoring. In addition, participants who report using nicotine products in the past 3 months, will be provided with a handout on the benefits of and tips for quitting smoking during or after pregnancy.

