7.2.3 Visit 3 or Day 3 or Post-test, etc. (If applicable)

Provide a description of what procedures will be performed on visit 2 or day 2 or post-test in order of how these will be done. If your study involves more than two sessions or visits replicate this section for each additional session or visit (e.g., 7.2.3, 7.2.4, etc.).

Study Visit 3 (V3) as summarized in Table 1 will take place about 3 to 4 months after the participants first study visit. At this visit, participants will receive “Physical Activity After Pregnancy” handouts that includes information on safely adding physical activity into their daily life from their visiting nurse. The NFP visiting nurse will also answer any questions participants have about physical activity and weight monitoring. The NFP visiting nurse will also review results and answer any questions about the results from participant home blood pressure monitoring. In addition, participants who report using nicotine products in the past 3 months, will be provided with a handout on the benefits of and tips for quitting smoking during or after pregnancy.

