7.3 Duration of Participation

Describe how long subjects will be involved in this research study. Include the number of sessions and the duration of each session - consider the total number of minutes, hours, days, months, years, etc.

Participation in this study will take about 6 months. It is anticipated that Visit 1 will last approximately 45 minutes, 15 minutes for the questions and 30 minutes to instruct in the use of the devices. This may be divided among consecutive visits based on standard care.

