13.0 Subject Payment and/or Travel Reimbursements

Describe the amount, type (cash, check, gift card, other) and timing of any subject payment or travel reimbursement. If there is **no** subject payment or travel reimbursement, indicate as not applicable.

Extra or Course Credit: Describe the amount of credit **and** the available alternatives. Alternatives should be equal in time and effort to the amount of course or extra credit offered. It is not acceptable to indicate that the amount of credit is to be determined or at the discretion of the instructor of the course.

Approved Subject Pool: Indicate which approved subject pool will be used; include in response below that course credit will be given and alternatives will be offered as per the approved subject pool procedures.

Participants are eligible to receive up to \$300. Participants will receive \$100.00 after completing the first study visit and baseline survey. Upon completing the second study visit, participants will receive \$100.00. Upon completing the last study visit and follow-up survey, participants will receive \$100.00. Participants will also get to keep the Fitbit and Fitbit Scale they have used during the study.

****Site Congruency: Is the information provided in the above section (Subject Payment and/or Travel Reimbursements) consistent across all relying sites in this research?**

Yes

No - Identify the sites that have dissimilar procedures: *[This field should solely identify the site. Dissimilar procedures across sites should be identified in the SITE workspace via HRP-XXX – R2S Site Plan]*

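### Home BP monitoring is planned for 6 months, but the last scheduled study step is V3 and no later log collection is set, so 6-month and postpartum uptake may not be measurable

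*Combined protocol and SAP*

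**What the plan says.** - **Monitoring period.** Section 7.2.1 provides "a home blood pressure monitor that monitors your blood pressure three times per week for 6 months". The HBPM paragraph of section 7.2 adds the content of a session: "Participants will be asked to self-monitor their BP 3 times per week, to take 2 readings each time". Section 7.3 states "Participation in this study will take about 6 months".
- **Study visits.** There are three. V2 "will take place about 1 to 2 months after the participants first study visit" (section 7.2.2) and V3 "will take place about 3 to 4 months after the participants first study visit" (section 7.2.3). Table 1 heads the V3 column +2 months and has no later column, so its last HBPM entry is at V3.
- **Follow-up survey and last payment.** Table 1 places the follow-up and satisfaction surveys at V3. The text of section 7.2 puts the follow-up questionnaires after V3 without naming a month. Section 13.0 makes the final $100 depend on both: "Upon completing the last study visit and follow-up survey, participants will receive" it.
- **The log.** Section 7.2 has participants write readings on a study log, which the nurse reviews at every home visit and uses for referral. Section 6.2.1.2 describes the log as paper. Section 17.3 covers electronic data and storage of paper records but not the return of logs.
- **The endpoint.** Section 1.3 names uptake and utility of "intermittent home-based blood pressure monitoring (HBPM) during and after pregnancy". Sections 1.3 and 8.3 give no measure, window or denominator for uptake.
- **Intervention period.** Sections 7.1 and 7.2 describe enhanced care up to 6 months postpartum, starting as early as the first trimester.

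**The concern.** The monitoring period and the study's own schedule end at different times. If the log is read into the data only as far as V3, the planned 6 months of self-monitoring are not observed in full. Sustained use is one of the main things a feasibility pilot should tell the designers of the larger trial mentioned in section 11.2.

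The postpartum part of the endpoint is the more exposed. Section 2.1 presents blood pressure across the transition from pregnancy to postpartum as novel data. Women are recruited before 28 weeks, so a cut at V3 would come before or soon after delivery. The log also matters because section 7.2 says that no research data are taken from the Fitbit or the scale.

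**Working it through.** The documents give no uptake figure to reproduce, so the check is on timing.

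**1. Sessions after V3.** Inputs: 3 sessions a week for 6 months (7.2.1), 2 readings per session (7.2), V3 at month 3 to 4 (7.2.3) or +2 months (Table 1). With 52/12 = 4.33 weeks per month, 6 months is 26 weeks: 26 × 3 = 78 sessions and 78 × 2 = 156 readings. The share after V3 at month t is (6 − t)/6.

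| V3 at month | Sessions due by V3 | Sessions after V3 | Share after V3 |
|---|---|---|---|
| 4 | 52 | 26 | 33% |
| 3 | 39 | 39 | 50% |
| 2 (Table 1 counted from entry) | 26 | 52 | 67% |

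If Table 1's +2 months is counted from V2 (month 1 to 2), V3 falls at 1 + 2 = 3 to 2 + 2 = 4 months and agrees with section 7.2.3.

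**2. Direction of error if logs stop at V3.** Let adherence be a before V3 and b after it. Both are assumptions, as the documents give neither.

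- True 6-month uptake = [a·t + b·(6 − t)]/6.
- Denominator also stopped at V3: the estimate is a, with error (a − b)(6 − t)/6.
- Denominator kept at 6 months: the estimate is a·t/6, with error −b(6 − t)/6.

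| Assumed a, b | V3 month | True uptake | Error, V3 denominator | Error, 6-month denominator |
|---|---|---|---|---|
| 80%, 80% | 3 | 80% | 0 | −40 points |
| 80%, 80% | 4 | 80% | 0 | −27 points |
| 80%, 40% | 3 | 60% | +20 points | −20 points |
| 80%, 40% | 4 | 67% | +13 points | −13 points |
| 60%, 80% | 3 | 70% | −10 points | −40 points |
| 60%, 80% | 4 | 67% | −7 points | −27 points |

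The sign depends on the denominator and on whether adherence falls or rises. If logs are kept and collected to month 6, there is no truncation error.

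**3. Postpartum readings.** This needs no adherence assumption. Assume delivery at 40 weeks and V1 at the gestation of enrolment. Recruitment is before 28 weeks (4.2.3).

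- V3 at month 3 (13 weeks): postpartum readings only if entry is after 40 − 13 = 27 weeks. A woman entering just before 28 weeks has at most 28 + 13 − 40 = 1 week (3 sessions).
- V3 at month 4 (17.3 weeks): entry after 40 − 17.3 = 22.7 weeks. The maximum is 28 + 17.3 − 40 = 5.3 weeks (16 sessions).
- V3 at month 2 (8.7 weeks): 28 + 8.7 = 36.7 weeks, so no woman has any.
- Month 6 (26 weeks): entry after 40 − 26 = 14 weeks. The maximum is 28 + 26 − 40 = 14 weeks (42 sessions).

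Earlier delivery lowers each threshold week for week. At 37 weeks the V3 thresholds are 24 and 19.7 weeks, and the maximum by V3 is 8.3 weeks.

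**4. Six months from entry against 6 months postpartum.** With delivery at 40 weeks, 6 months postpartum is 40 + 26 = 66 weeks. That is 66 − 28 = 38 weeks after entry for the latest entrants and 66 − 12 = 54 weeks for a woman entering at 12 weeks, against 26 weeks of monitoring from V1.

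**The case against.** A reader might infer more than the documents support, in four ways.

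- **That reported uptake would be overstated.** This needs adherence to fall after V3, and both the log data and the denominator to stop there. The protocol states none of these, and the error reverses with a 6-month denominator.
- **That the months after V3 lie outside the study.** The nurses are study personnel (5.2.1), the log is a study document, and they review it at every home visit. Those visits are more frequent than V1 to V3 and continue well after delivery (2.1). Section 7.2 also adopts an earlier trial programme's apps and central database, which might be a second route for readings, though how it fits with a paper log is not explained.
- **That the survey and last payment are fixed at 3 to 4 months, so adherence will drop once payment ends.** Section 7.2 says only that the survey follows V3, and section 13.0 pays for visits and surveys, not for logging.
- **That the log cannot show utility.** The template bars data-collection materials from the protocol, so the log's columns cannot be seen.

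It is also true that the protocol does not say the log is taken in at V3. Its transfer is unspecified at every time point, and a cut at V3 is one possible reading. Nor would collection at month 6 give every woman postpartum readings. Finally, this is a secondary endpoint without a threshold, in a descriptive pilot of 20 women.

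All of this stands. It does not supply a dated log return after V3, and review for referral is not described as data capture.

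**Conclusion.** The mismatch is real. On section 7.2.3's timing, one third to one half of the planned sessions fall after the last scheduled study step; on the month-2 reading of Table 1, two thirds do. If logs are taken in only to V3, uptake over the planned 6 months cannot be determined. No direction of bias can be claimed, and the percentage-point errors shown rest wholly on assumed adherence.

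The firmer consequence is postpartum coverage. With a cut at V3 and delivery at 40 weeks, women entering before 27 weeks (V3 at month 3) or 22.7 weeks (V3 at month 4) contribute nothing postpartum, and the latest entrants contribute at most about 5 weeks. How many of the 20 this affects depends on gestation at entry, which the documents do not give. The point is worth correcting because the remedy is cheap, but it does not threaten the primary endpoints.

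**What to change.** 1. Reconcile Table 1's +2 months with the V3 timing in section 7.2.3, and both with the 6-month period in sections 7.2.1 and 7.3 and the care up to 6 months postpartum in sections 7.1 and 7.2. State the reference point for each time.
2. Add a Table 1 column for collection of the BP log by the nurse at the routine NFP visit nearest month 6, and say how and when logs reach the study team. State whether the app and central database also supply readings.
3. In section 8.3, define HBPM uptake as sessions logged out of the 78 planned, split before and after V3 and by pregnant or postpartum status. Women entering before about 14 weeks may still have no postpartum readings at month 6, so report how many women contribute to each part.
4. If the log does not already record them, capture whether a third reading was taken and a referral given, and report these as the measure of utility.

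No extra visit is needed. The cost is a little nurse time, possibly a revised log sheet, and perhaps a less favourable uptake figure.

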7.2.2 Visit 2 or Day 2 or Post-test, etc. (If applicable)

Provide a description of what procedures will be performed on visit 2 or day 2 or post-test in order of how these will be done. If your study involves more than two sessions or visits replicate this section for each additional session or visit (e.g., 7.2.3, 7.2.4, etc.).

Study Visit 2 (V2) as summarized in Table 1 will take place about 1 to 2 months after the participants first study visit. At this visit, participants will receive “Physical Activity During Pregnancy” handouts that includes information on safely adding physical activity into their daily life from their visiting nurse. The NFP visiting nurse will also answer any questions participants have about physical activity and weight monitoring. The NFP visiting nurse will also review results and answer any questions about the results from participant home blood pressure monitoring. In addition, participants who report using nicotine products in the past 3 months, will be provided with a handout on the benefits of and tips for quitting smoking during or after pregnancy.

7.2.3 Visit 3 or Day 3 or Post-test, etc. (If applicable)

Provide a description of what procedures will be performed on visit 2 or day 2 or post-test in order of how these will be done. If your study involves more than two sessions or visits replicate this section for each additional session or visit (e.g., 7.2.3, 7.2.4, etc.).

Study Visit 3 (V3) as summarized in Table 1 will take place about 3 to 4 months after the participants first study visit. At this visit, participants will receive “Physical Activity After Pregnancy” handouts that includes information on safely adding physical activity into their daily life from their visiting nurse. The NFP visiting nurse will also answer any questions participants have about physical activity and weight monitoring. The NFP visiting nurse will also review results and answer any questions about the results from participant home blood pressure monitoring. In addition, participants who report using nicotine products in the past 3 months, will be provided with a handout on the benefits of and tips for quitting smoking during or after pregnancy.

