4.2 Recruitment process

Describe how potential subjects first learn about this research opportunity or indicate as not applicable if subjects will not be prospectively recruited to participant in the research. Subject recruitment can involve various methods (e.g., approaching potential subjects in person, contacting potential subjects via email, letters, telephone, ResearchMatch, or advertising to a general public via flyers, websites, StudyFinder, newspaper, television, and radio etc.). **DO NOT** include the actual recruitment material or wording in this protocol.

[Do not type here]

4.2.1 How potential subjects will be recruited.

Potential participants will be recruited through established partnerships with Geisinger and UPMC Nurse Family Partnership agencies. After potential participants are identified by visiting nurses and/or their supervisors, visiting nurses will share information about the pilot study verbally and through a written summary handout prepared by the study team.

4.2.2 Where potential subjects will be recruited.

Potential participants will be recruited in their own homes during regularly scheduled home visits with their NFP visiting nurse.

4.2.3 When potential subjects will be recruited.

Potential participants will be recruited during pregnancy (<28 weeks' gestation) during regularly scheduled home visits with their visiting nurse from NFP.

4.2.4 Describe the eligibility screening process and indicate whether the screening process will occur before or after obtaining informed consent. Screening begins when the investigator obtains information about or from a prospective participant in order to determine their eligibility. In some studies, these procedures may not take place unless HIPAA Authorization is obtained OR a waiver of HIPAA Authorization when applicable for the screening procedures is approved by the IRB. [For FDA regulated studies, consent for any screening activities would need to be obtained prior to screening unless specifically waived by the IRB.]

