7.2 Study Procedures

Provide a step by step description of all research procedures being conducted (broken down by visit, if applicable) including such information as below (where and when applicable); describe the following:

- HOW: (e.g., data collection via interviews, focus groups, forms such as surveys and questionnaires, medical/school records, audio/video/digital recordings, photographs, EKG procedures, MRI, mobile

- devices such as electronic tablets/cell phones, observations, collection of specimens, experimental drug/device testing, manipulation of behavior/use of deception, computer games, etc.)
- WHERE: (e.g., classrooms, labs, internet/online, places of business, medical settings, public spaces, etc.)

Intervention Overview. Our pilot CVH intervention will be delivered by NFP visiting nurses starting as early as NFP program enrollment in the first trimester after confirmation of a viable pregnancy and no later than the 28th week of pregnancy and will continue up to 6 months postpartum. The visit schedule will be consistent with the NFP program visit structure to deliver intervention content at regularly scheduled visits that are typically 60 minutes long (weekly visits for the first month following enrollment followed by twice monthly visits until delivery).

The pilot intervention will include a behavioral component aimed at reducing sedentary behaviors as well as utilizing a technology/monitoring component. We will monitor all mothers with a wrist-worn actigraphy device (FitBit) to record activity and sleep, weight scale (Fitbit Scale), intermittent home ambulatory blood pressure self-monitoring (HBPM), and carbon monoxide monitoring administered by the NFP visiting nurse. Carbon monoxide monitoring is part of an attempt to reduce the use of nicotine-containing products. Monitoring with digital devices is discussed below and in the digital device section which follows a description of the interventions. However, the participant will have access to the digital data on the device through smartphone or computer apps to reinforce desired behaviors.

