CONSTRUCT	MEASURE	Prenatal and/or Postpartum		
		Study entry (V1)	+ 1 month (V2)	+2 months (V3)
Smoking status	National Adult Smoking Survey questions	S	S	S
Home Blood Pressure Monitoring (HBPM)	Systolic/diastolic blood pressure three times a week; nurse review results at each visit and provide referrals for high readings	C / N	C / N	C / N
Carbon Monoxide (CO) Monitoring	CO monitoring will take place to monitor for smoke exposure, faulty ventilation, etc.	N	N	N
Physical Activity	Sedentary time, steps, intensity, hours/week monitored by actigraphy device	C	C	C
Demographic/baseline characteristics	Developed for ENRICH	S		S
Satisfaction	Developed for ENRICH			S

S=survey; C= client self-monitoring; N= nurse administered

MATERNAL MODIFIED AMERICAN HEART ASSOCIATION HEALTH INDICATORS

Smoking. Maternal smoking status will be assessed at baseline using items from the National Adult Smoking Survey including: “Have you ever smoked a cigarette, even one or two puffs?”; “About how many cigarettes have you smoked in your entire life?”; “During the past 30 days, on how many days did you smoke cigarettes?”; “When was the last time you smoked a cigarette, even one or two puffs?”; and “During the past 30 days, on the days you smoked, about how many cigarettes did you smoke per day?” A script is provided for the NFP nurse to administer this intervention. This will be repeated at the designated time points in Table 1 among known smokers only.

DIGITAL DEVICE MONITORING

Our plan will be to use digital devices that can be accessed through apps on participant smart phones. The participants will have immediate access to the data from the Fitbit and Fitbit Scale, through Bluetooth links to their smartphone or computer. Research data will not be collected from these devices (i.e., the research team will not have access to data from the Fitbit or Fitbit Scale). However, NFP home visiting nurse will answer any questions related to physical activity and weight as standard care. The research team will ask participants to document readings from the blood pressure monitor on a study tracking log. This log will be reviewed by the NFP visiting nurse at each home visit and referral provided for high readings as appropriate (details below).

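### Visit 3 and the only satisfaction survey are timed from study entry, not delivery, so participants' own rating of the postpartum content is not assured

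*Combined protocol and SAP*

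**What the plan says.** **Visit timing.** Section 7.2.1 places V1 at the first home visit after consent. Section 7.2.2 states: "Study Visit 2 (V2) as summarized in Table 1 will take place about 1 to 2 months after the participants first study visit". Section 7.2.3 states: "Study Visit 3 (V3) as summarized in Table 1 will take place about 3 to 4 months after the participants first study visit". V3 is the visit at which the "Physical Activity After Pregnancy" handout is given, and section 13.0 treats it as the last study visit. Table 1 heads the visit columns "Prenatal and/or Postpartum", so visits may fall on either side of delivery.

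**Entry.** Section 7.2 describes delivery of the module "starting as early as NFP program enrollment in the first trimester after confirmation of a viable pregnancy". Section 4.2.3 sets the upper limit: "Potential participants will be recruited during pregnancy (<28 weeks".

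**Survey.** Table 1 has one satisfaction mark, in the V3 column. The follow-up demographics mark is in the same column, and the text of section 7.2 places that collection "at follow-up (after study visit 3", with no interval given. The same paragraph adds: "Participants will be asked to provide information about their pregnancy and household and complete two online packets of questionnaires".

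**Endpoint, duration and analysis.** Section 1.2 makes good acceptability of the module, to nurses and to participants, a primary endpoint. Integration of the module up to 6 months after delivery is another. Section 7.3 gives participation as about 6 months. Section 8.3 plans descriptive statistics only and names satisfaction as an example of acceptability.

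**The concern.** The module has postpartum content of its own. Section 7.2 aims to raise activity after delivery and sets a target of 150 minutes of exercise per week in the puerperium. Aim 4 concerns postpartum activity, and Aim 2 covers acceptability and delivery for both pregnant and postpartum women.

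The V3 rule, followed exactly, hands postpartum material to some women while they are pregnant. A woman who answers the satisfaction survey before delivery cannot rate content she has not used. Section 8.3 does not say that satisfaction will be shown by pregnancy status, so one summary from 20 women could mix ratings made before and after delivery. That summary would then be read as acceptability of the whole module, and section 11.2 says the pilot is meant to inform a large multi-site trial.

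**Working it through.** The plan gives no figure to reproduce on this point: section 8.2 states that no formal sample size calculation was done. The check is date arithmetic.

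**Inputs from the protocol.** V3 at 3 to 4 months after V1 (7.2.3); participation about 6 months (7.3); entry from the first trimester to under 28 weeks (7.2, 4.2.3); 20 women (8.1); weekly home visits for 6 weeks after delivery (2.1).

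**Assumptions.** Delivery at 40 weeks, with 37 and 39 shown as a range; 4.348 weeks per month; entry distributions as stated below.

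**Step 1: is Table 1 consistent with the text?** Table 1 labels V2 as plus 1 month and V3 as plus 2 months. Read as increments, V2 is at 1 to 2 months, and adding 2 gives V3 at 3 to 4 months. This matches section 7.2.3, so the text timing is used.

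**Step 2: who is still pregnant?** A woman is still pregnant at a given time if her gestational age at V1 is below the week of delivery minus the weeks elapsed. Three, 4, 5 and 6 months are 13.0, 17.4, 21.7 and 26.1 weeks.

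| Time from V1 | Delivery at 40 weeks | at 39 weeks | at 37 weeks |
|---|---|---|---|
| 3 months (early V3) | entry before 27.0 | 26.0 | 24.0 |
| 4 months (late V3) | 22.6 | 21.6 | 19.6 |
| 5 months | 18.3 | 17.3 | 15.3 |
| 6 months (end) | 13.9 | 12.9 | 10.9 |

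With delivery at 40 weeks, anyone entering before 22.6 weeks is pregnant throughout the V3 window. Entry at 12 weeks puts V3 at 12 + 13.0 = 25.0 to 12 + 17.4 = 29.4 weeks, and the end of participation at 12 + 26.1 = 38.1 weeks.

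**Step 3: illustrative shares still pregnant when surveyed.** These take delivery at 40 weeks and entry uniform over the stated weeks. They are scenarios, not estimates.

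| Survey time | Entry 8–28 weeks | Entry 20–28 | Entry 24–28 |
|---|---|---|---|
| At V3 (uniform over 3–4 months) | 84% (about 17 of 20) | 60% (about 12) | 25% (about 5) |
| 5 months | 51% (about 10) | 0% | 0% |
| 6 months | 30% (about 6) | 0% | 0% |

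For the first column, the mean threshold over 3 to 4 months is (27.0 + 22.6)/2 = 24.8, giving (24.8 − 8)/20 = 84%. At 5 months, (18.3 − 8)/20 = 51%. At 6 months, (13.9 − 8)/20 = 30%. For entry over 20–28 weeks at V3, (24.8 − 20)/8 = 60%. For 24–28 weeks, averaging max(0, (t − 24)/4) over thresholds t from 22.6 to 27.0 gives 25%. With delivery at 38 weeks the V3 row becomes 74%, 35% and 3%, and the 6-month row 20%, 0% and 0%.

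**Step 4: does a survey at 6 weeks postpartum fit within 6 months?** Week 46 is (46 − 20)/4.348 = 6.0 months after entry at 20 weeks, so it fits for entry at 20 weeks or later. For earlier entry it does not: 6.9 months at 16 weeks, 7.8 at 12 and 8.7 at 8. Entry at 16 weeks still reaches 16 + 26.1 = 42.1 weeks, about 2 weeks postpartum, by the end of the 6 months.

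**The case against.** The strongest reply has four parts.

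- **The survey probably comes later than V3.** The follow-up demographics mark also sits in the V3 column, yet the text places that collection after V3. The satisfaction mark most naturally means the same packet. This stands. The V3 row of Step 3 is therefore a worst case, and its 84% also needs uniform entry from 8 weeks, which nothing in the protocol supports. A reader might infer that most of the 20 women will be surveyed while pregnant; the documents do not show that.
- **The endpoint is wider than one rating.** Satisfaction is only an example of acceptability, nurses record delivery quality and participant engagement, and their visits continue after delivery. This also stands, so it would be wrong to infer that the postpartum content goes unobserved. Nurse records are not participant ratings, however, and section 1.2 names both groups.
- **Timing from entry is a legitimate choice.** Table 1's column heading shows that visits on either side of delivery were foreseen, and an early handout can serve as advance guidance. Early issue is not an error in itself. What remains is that a woman cannot rate what she has not yet used.
- **The survey form is not in the protocol.** Its items are unknown, and the packets ask about the pregnancy, so status at the survey may be known. That makes separate reporting easy, but section 8.3 does not provide for it.

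A reader might also see a conflict between Table 1's plus 2 months and the 3 to 4 months of section 7.2.3. Step 1 shows that the two agree when read as increments, so no conflict is claimed.

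**Conclusion.** The concern holds as a minor design point. Neither V3 nor the satisfaction survey is tied to delivery, so a participant rating of the postpartum content is not assured. With delivery at 40 weeks, women entering before about 22.6 weeks receive the postpartum handout while pregnant. Those entering before about 13.9 weeks would still be pregnant at the survey even if it waited until the end of their 6 months. These limits rest on the assumed delivery week and fall by 3 weeks if delivery is at 37 weeks.

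The number of women affected cannot be stated, because the entry distribution and the packet date are not given. It could be nil: with entry at 20 weeks or later and a packet at 5 to 6 months, every woman delivering by 40 weeks is surveyed after delivery. The documents do not support a claim that the acceptability endpoint as a whole fails.

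**What to change.** Amend sections 7.2 and 7.2.3 as follows.

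1. Where delivery falls within the 6-month participation, give the V3 handout at an existing weekly home visit soon after delivery. Give the satisfaction packet at a later visit within the 6 weeks of weekly postpartum visits, or at the end of the 6 months if that comes first.
2. For women who entered too early for this, keep the 6-month limit and give the packet at its end.
3. For all women, record the delivery date and the pregnancy status at the survey.
4. In section 8.3, state that satisfaction will be reported separately for women surveyed before and after delivery, and that the postpartum acceptability conclusion is limited to those surveyed after delivery.

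**Cost.** A short amendment, a more variable V3 date, a final payment that may come later but still within the 6 months, and fewer women contributing to the postpartum rating. No home visit is added. The rating would cover early postpartum content, not the full period up to 6 months after delivery.

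Surveying every woman at 6 weeks postpartum is not recommended. It would stretch participation to between 6.9 and 8.7 months for entry at 16 down to 8 weeks, in a pilot that section 3.3.2 limits to about 12 months.
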